## 8.7 Adjustment of Dose

Dose frequency adjustments for platelet count reduction must be made in accordance with [Section 8.6.3](#) and [Table 3](#) (above).

Other dose adjustments, including dose interruptions, and/or decreasing the dose will be allowed for safety or tolerability after consultation with the Sponsor Medical Monitor.

Patients may have their dose interrupted in response to AEs after consultation with Study Medical Monitor.

## 8.8 Discontinuation of Study Drug

A patient must permanently discontinue study treatment for any of the following:

- The patient becomes pregnant. Report the pregnancy according to instructions in [Section 9.5.4](#)
- The patient withdraws consent
- The patient experiences an AE that necessitates permanent discontinuation of Study Drug
- The patient develops laboratory test abnormalities that meet any of the stopping rules listed in [Sections 8.6.1](#) to 8.6.3
- When a platelet count of less than 50,000/mm^3, or a platelet count less than 75,000/mm^3 while the patient is on a reduced dose.

The reason for discontinuation of Study Drug must be recorded in the electronic Case Report Form (eCRF) and source documentation.

### 8.8.1 *Follow-up Visits for Early Termination from Treatment Period or from Post-Treatment Follow-up Period*

Any patient who discontinues early from the treatment period or from post-treatment follow-up period should be followed as per the platelet monitoring rules shown in [Table 3](#), [Section 8.6.3](#) for the first 6 weeks after discontinuing Study Drug. Following this period, if the platelet count is stable (at least 3 consecutive values that are stable as determined by the Sponsor Medical Monitor and > 100,000/mm^3), the next platelet count should be taken within at least 6 weeks so that patients are monitored for at least 12 weeks after discontinuing Study Drug.

Following 6 weeks of Study Drug discontinuation, patients should be strongly encouraged to attend planned Study Center visits (including End-of-Treatment Week 53 visit and final Post-Treatment Follow-up visit 16 weeks after their last dose of Study Drug) to collect the study assessments in accordance with the Schedule of Procedures in [Appendix A](#).

If the patient declines or is unable to participate in the above, an ET visit (Week 53 visit assessments) should be performed at the time of withdrawal, at a minimum, and ideally within 2 weeks from the last dose of Study Drug.

## 8.9 Withdrawal of Patients from the Study

Patients must be withdrawn from the study for any of the following:

- Withdrawal of consent
- The patient is unwilling or unable to comply with the protocol
- The patient permanently discontinues Study Drug (see [Section 8.8](#))
- The patient meets any of the Exclusion Criteria (see [Section 5.2](#)) after enrolling in the study that in the opinion of the Investigator represents a safety risk to the patient

Other reasons for withdrawal of patients from the study might include:

- At the discretion of the Investigator for medical reasons
- At the discretion of the Investigator or Sponsor for noncompliance
- Significant protocol deviation

All efforts will be made to complete and report the observations as thoroughly as possible up to the date of withdrawal. All information, including the reason for withdrawal from study, must be recorded in the eCRF.

Any patient who withdraws consent to participate in the study will be removed from further treatment and study observation immediately upon the date of request. These patients should be encouraged to complete the ET study procedures and observations at the time of withdrawal ([Appendix A](#)).

For patients withdrawn for reasons other than withdrawal of consent every effort should be made to complete the ET study procedures and observations at the time of withdrawal (see [Appendix A](#)).

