#### **3.4.3 Post-Treatment**

Patients when completed dosing will enter the 16-week post-treatment follow-up period and will return to the Study Center for 3 follow-up visits 4, 10, and 16 weeks after their last injection of Study Drug as per Appendix A (Follow-up).

The final study visit for each patient will be 16 weeks after the last dose of Study Drug.

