## 8.5 Safety Monitoring Rules

Please refer also to the “Guidance for Investigator” section of the Investigator’s Brochure.

For the purposes of safety monitoring baseline is defined as the average of the pre-dose test closest to Day 1 and the Day 1 value itself.

In addition to the standard monitoring of clinical safety parameters, the following guidelines are provided for the monitoring of selected parameters chosen based on preclinical and clinical observations.

In case of discrepancy between the test results from 2 sources, such as between the central and local lab, safety-mandated action must be initiated based on the more critical (lower or higher, as relevant) of the 2 values.

Confirmation Guidance: At any time during the study (treatment or post-treatment follow-up periods), the clinical laboratory results meeting any of the safety monitoring criteria presented below **must be confirmed** by performing measurements (ideally in the same laboratory that performed the initial measurement) on new specimens prior to administering the next dose of

Study Drug (ISIS 681257 or placebo). All new specimen collections should take place as soon as possible (ideally within 3 days of the initial collection).

In addition, as described in [Section 6.2.1](#) hematology labs should be sent in parallel to the central and local laboratory for analysis.

Stopping Rule Guidance: The Investigator may interrupt or permanently discontinue study treatment for any medical reason including changes in clinical laboratory results.

In the event of an initial clinical laboratory result that meets a stopping criterion, patients must not be re-dosed until a confirmatory test result has been reviewed by the Study Medical Monitor. If any of the stopping criteria described below (refer to [Sections 8.6.1](#) to [8.6.3](#)) are met and are confirmed, the patient will be permanently discontinued from further treatment with Study Drug (ISIS 681257 or placebo), evaluated fully as outlined below and in consultation with the Study Medical Monitor or appropriately qualified designee, and will be entered into the post-treatment evaluation portion of the study. In general, patients who do not meet the stopping rules based upon retest may continue dosing. However, the Investigator and the Study Medical Monitor (or appropriately qualified designee) should confer as to whether additional close monitoring of the patient is appropriate.

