#### **9.5.4 Contraception and Pregnancy**

Male and female patients of childbearing potential must continue to use appropriate contraception with their partners, or refrain from sexual activity, as described in [Section 6.3.1](#).

If a patient becomes pregnant or a pregnancy is suspected, or if a male patient makes or believes that he has made someone pregnant during the study, then the Study Center staff must be informed immediately. An Initial Pregnancy Form should be submitted to the Sponsor or designee **within 24 hours** of first learning of the occurrence of pregnancy. Follow-up information including delivery or termination is reported by designating as ‘Follow-up’ on the Pregnancy Forms and reported within 24 hours of occurrence.

Payment for all aspects of obstetrical care, child or related care will be the patient’s responsibility.

Female patients: If a suspected pregnancy occurs while on the study (including during the follow-up period), a pregnancy test will be performed. The patient with a confirmed pregnancy will be immediately withdrawn from treatment with Study Drug. However, the patient will be encouraged to complete the Post-treatment Follow-up portion of the study to the extent that study procedures do not interfere with the pregnancy. Regardless of continued study participation, the Investigator will assist the patient in getting obstetrical care and the progress of the pregnancy will be followed until the outcome of the pregnancy is known (i.e., delivery, elective termination, or spontaneous abortion). If the pregnancy results in the birth of a child, the Study Center and Sponsor may require access to the mother and infant’s medical records for an additional 8 weeks after birth. Follow-up will be performed to the extent permitted by the applicable regulations and privacy considerations.

Male patients: The progress of the pregnancy of a male patient’s partner should be followed until the outcome of the pregnancy is known (i.e., delivery, elective termination, or spontaneous abortion). If the pregnancy results in the birth of a child, **the Study Center and Sponsor may request access to the mother and infant’s medical records for an additional 8 weeks after birth.** Follow-up will be performed to the extent permitted by the applicable regulations and privacy considerations.

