### **10.6.3 Efficacy Analysis**

#### **10.6.3.1 Analysis of Primary Efficacy Endpoint**

The primary analysis of the primary endpoint will be the pairwise comparison of percent change from baseline to primary analysis time point in fasting Lp(a) between ISIS 681257 treatment groups and pooled placebo group in the FAS. The data will be analyzed using an analysis of covariance (ANCOVA) model with the Baseline Lp(a) as a covariate. Missing data may be handled by LOCF or multiple imputation methods ([Schafer 1997](#); [Schafer 1999](#)).

The primary efficacy analysis will take place after the last patient has completed the primary analysis time point and at least 50% of randomized patients have completed Week 52 visits, and the database has been locked,

The following sensitivity analyses will be conducted:

- The primary analysis will be repeated in the PPS
- The primary efficacy endpoint will be analyzed using a Wilcoxon Rank Sum test on both FAS and PPS, and the treatment effect will be estimated using Hodges-Lehmann estimator

Additional sensitivity analyses may be conducted as appropriate; the details of these analyses will be outlined in the SAP.

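### Section 8.9 requires patients who stop Study Drug to leave the study, against Sections 8.8.1, 8.5 and 9.5.4; read literally, it loses the Week 25/27 Lp(a) of anyone who stops earlier

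*Protocol*

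**What the plan says.** Section 8.9 opens its compulsory list with "Patients must be withdrawn from the study for any of the following", and one entry is "The patient permanently discontinues Study Drug". A second list in that section gives reasons that might lead to withdrawal, so the compulsory wording looks intended. For patients withdrawn other than by withdrawing consent, the only data it asks for are that "every effort should be made to complete the ET study procedures and observations at the time of withdrawal".

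Three other sections treat the same patients differently:

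- Section 8.8.1 has early discontinuers followed for platelets for at least 12 weeks. After 6 weeks off drug, "patients should be strongly encouraged to attend planned Study Center visits", with the Appendix A assessments. The early termination visit, ideally within 2 weeks of the last dose, is only the fallback for those who decline or cannot attend.
- Section 8.5 says that a patient with a confirmed stopping criterion "will be entered into the post-treatment evaluation portion of the study". Section 3.4.3 defines that period as "3 follow-up visits 4, 10, and 16 weeks after their last injection of Study Drug".
- Section 9.5.4 says of a pregnant patient taken off drug that "the patient will be encouraged to complete the Post-treatment Follow-up portion of the study".

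On analysis, Section 10.6.3.1 states "Missing data may be handled by LOCF or multiple imputation methods". Section 10.3 presents the FAS as the feasible intent-to-treat population and uses it for the primary efficacy analysis.

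**The concern.** A site cannot both withdraw a patient from the study and keep that patient in follow-up, so the outcome depends on which section the site reads. The choice decides whether data exist, and no analysis plan can recover a sample that was never taken.

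Under the literal reading of 8.9, a patient who stops before the primary time point contributes no Lp(a) at Week 25/27. The last value is the early termination sample, which includes Lp(a) through the PD panel (Appendices A and B). Carrying it forward credits the drug with a suppression that would largely have worn off. Multiple imputation does not cure this by itself: if no off-drug values are kept, it borrows mainly from patients still on drug. The literal reading also ends the platelet follow-up that 8.8.1 requires, which is a separate reason to reconcile the sections.

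**Working it through.** **Design figure.** The protocol gives no figure on this point. Its related figure is the power statement in Section 10.2: 23 against 23, difference 20, SD 20, two-sided 0.05. The noncentrality is 20 / (20 × √(2/23)) = 3.39, and the noncentral t power is 91.2%, in line with the stated 90% or so. It is not in dispute.

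**Inputs from the protocol.** Half-life h of 3 to 4 weeks (Section 2.3.4). Predicted reduction Rmax of 60% to 85% at steady state (Section 2.4). Primary time point Week 25 or 27 (Section 10.1). No replacement of withdrawn patients (Section 4.3).

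**Assumptions.** The fraction d of an active arm stopping before the time point is 5% to 20%. Stopping weeks s are uniform from 0.5 to 24.5. Lp(a) responds and recovers at rate h, with h = 8 weeks as a slow check.

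**Model.**

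- On-drug reduction at stopping: R(s) = Rmax × (1 − 2^(−s/h)).
- Off-drug reduction at Week 25: R(s) × 2^(−(25−s)/h).
- Overstatement by LOCF: d × Rmax × F, where F is the mean over s of (1 − 2^(−s/h)) × (1 − 2^(−(25−s)/h)).
- F = 0.683 for h = 3, 0.579 for h = 4 and 0.309 for h = 8.

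**Results, in percentage points of mean reduction** (lower end Rmax 60, upper end Rmax 85):

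| d | h = 4 | h = 3 | h = 8 |
|---|---|---|---|
| 5% | 1.7 to 2.5 | 2.0 to 2.9 | 0.9 to 1.3 |
| 10% | 3.5 to 4.9 | 4.1 to 5.8 | 1.9 to 2.6 |
| 20% | 6.9 to 9.8 | 8.2 to 11.6 | 3.7 to 5.2 |

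For example, at d = 10%, Rmax 85 and h = 3: 0.10 × 85 × 0.683 = 5.8. Using Week 27 in place of Week 25 adds at most 0.5 points.

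**One patient.** Rmax 85, h = 4, stopping at Week 13: carried forward 85 × (1 − 2^(−13/4)) = 76%; off-drug at Week 25, 76.1 × 2^(−12/4) = 9.5%.

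**Is the early termination sample on-drug?** Two weeks after the last dose is inside the 4-week dosing interval, at the end of the 2-week interval and one week past the weekly one. One week past leaves 2^(−1/3) to 2^(−1/4), or 79% to 84%. If recovery is instead counted for two full weeks before the sample, the carried value falls to 2^(−2/3) to 2^(−2/4) of R(s), or 63% to 71%. The excess at d = 10% then drops to about 2.1 to 3.2 points (F of 0.356 to 0.380).

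**If follow-up is kept.** Take a patient who stops 12 weeks before the time point and gives the 10-week post-dose Lp(a). The residual effect is 9.9% to 17.7% at 10 weeks and 6.3% to 12.5% at 12 weeks. The excess is 2.2 to 4.4 points for that patient, or 0.2 to 0.4 points in the arm mean at d = 10%. Most of the problem therefore exists only under the literal reading of 8.9.

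**The case against.** The strongest reply is that the harm needs two steps, neither of them settled: sites following 8.9 rather than the more specific 8.8.1, and the analysis plan choosing LOCF. Section 10.6.3.1 permits LOCF beside multiple imputation, and Section 10 leaves data-handling conventions to the SAP. That stands, so the numerical part is conditional. The contradiction is not.

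The word overstated also depends on the target. Against the effect had patients stayed on drug, LOCF understates slightly, by 0.5 to 4.9 points across the same scenarios. The intent-to-treat sentence in Section 10.3 describes who is in the FAS and does not say how values after stopping are used. The treatment-policy reading is the natural one for that label, but it is a reading.

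Stronger inferences are tempting, and the protocol does not support them:

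- **Every discontinuer loses the primary value.** Treatment runs up to 52 weeks, and anyone who stops after Week 25/27 already has it.
- **The excess is 5 to 8 points at 10% discontinuing.** That needs every patient to stop about 12 weeks before the time point at full steady-state effect: 0.10 × 60 × 0.875 = 5.3 up to 0.10 × 85 × 0.9375 = 8.0.
- **The bias is largest in the higher-dose cohorts.** No stopping rate by cohort is given, and Section 2.3.4 reports that Phase 1 platelet fluctuations did not appear dose related. A gradient is possible, not shown.

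**Conclusion.** Section 8.9 is wrong as written: it cannot be followed together with 8.8.1, 8.5 and 9.5.4, and its literal reading removes the primary Lp(a) of patients who stop before Week 25/27. If LOCF were then used, the reduction would exceed the treatment-policy effect by about 1.7 to 2.9 points at 5% discontinuing, 3.5 to 5.8 at 10% and 6.9 to 11.6 at 20%. With slower recovery the range is 0.9 to 5.2 over 5% to 20%. These figures rest on an assumed discontinuation rate, an assumed spread of stopping times, and Lp(a) recovery at the drug half-life.

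Predicted reductions of 60% to 85% lie far above the 20-point design difference, so significance against placebo is unlikely to change. Effect size is affected, and so is the dose comparison if stopping differs by cohort (Section 10.1.4). This should be fixed; it does not threaten the trial's main conclusion.

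**What to change.** Three changes, none of which touches a dose or a stopping rule:

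1. In Section 8.9, take permanent discontinuation of Study Drug off the compulsory list, so that stopping drug and leaving the study are separate events, consistent with 8.8.1 and 8.5.
2. State that fasting Lp(a) is collected at the scheduled Week 25 or Week 27 visit whatever the drug status, and that this value enters the FAS analysis. The first change alone does not secure it: the visits at 4, 10 and 16 weeks after the last dose are not tied to Week 25/27, and 8.8.1 encourages planned visits only after 6 weeks off drug. Patients less than 6 weeks off drug must be covered explicitly.
3. In Section 10.6.3.1, do not use LOCF of on-drug values as the primary missing-data method.

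The cost is protocol wording, one scheduled visit kept for patients who have stopped drug, and a slightly less favourable estimate. The first two changes must be made before the visits fall due, because a sample not taken cannot be recovered.

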## 8.10 Concomitant Therapy and Procedures

The use of concomitant therapies or procedures defined below must be recorded on the patient's eCRF. AEs related to administration of these therapies or procedures must also be documented on the appropriate eCRF.

### 8.10.1 Concomitant Therapy

A concomitant therapy is any non-protocol specified drug or substance (including over-the-counter medications, herbal medications and vitamin supplements) administered from the time the patient has signed the informed consent at screening to the end of the post-treatment follow-up period.

#### Allowed Concomitant Therapy

Use of the following is allowed only if the patient has been on a stable regimen for at least 4 weeks prior to screening and is planned to remain on a stable regimen through the end of the post-treatment follow-up period:

- Lipid lowering drugs (statins, ezetimibe, PCSK9 inhibitors, niacin, fibrates, fish oil, other products containing omega-3 fatty acids (including OTC preparations))
- Anti-platelet therapies
- Testosterone, estrogens, progesterone, growth hormone, or progestins.

### **Disallowed Concomitant Therapy**

Use of the following is disallowed:

- Warfarin, direct thrombin inhibitors or Factor Xa inhibitors
- Other experimental agents during the study including investigational drug, biological agent, or device within 1 month of Screening, or 5 half-lives of investigational agent, whichever is longer. This includes marketed agents at experimental dosages
- Treatment with any non-Ionis oligonucleotide (including siRNA) at any time or prior treatment with an Ionis oligonucleotide or siRNA within 9 months of screening. Patients that have previously received only 1 dose of an Ionis oligonucleotide as part of a clinical study may be included as long as  $\geq 4$  months has elapsed since dosing
- Lipoprotein apheresis

Patients should consult with the Site Investigator or designee prior to initiating any new medication, including non-prescription or herbal compounds or any other non-drug therapy.

#### **8.10.2 Concomitant Procedures**

A concomitant procedure is any therapeutic intervention (e.g., surgery/biopsy, physical therapy) or diagnostic assessment (e.g., blood gas measurement, bacterial cultures) performed between screening and the end of the post-treatment follow-up period.

#### **8.11 Treatment Compliance**

Compliance with treatment dosing is to be monitored and documented by the Study Center staff and recorded in the eCRF.

Patients or Study Center Staff will record treatment administered in a dosing diary that will be reviewed by Study Center staff and entered into the eCRF.

#### **8.12 Safety Monitoring Compliance**

Compliance with safety monitoring requirements and treatment stopping rules must be documented by the Study Center staff.

Patients and the Study Investigators are required to adhere to a strict program of monitoring of platelet count, and liver and renal function as described in [Section 6.2.1](#), [Sections 8.5.1-8.5.3](#), and [Sections 8.6.1-8.6.3](#).

Patients will be required to have platelet counts every 2 weeks for the duration of the study and must not receive Study Drug without an interpretable platelet count result in the prior 2 weeks, in

which case the Investigator must contact the patient to hold dosing until a new platelet count is obtained and reviewed, and will document this contact.

Patients will also be required to have renal function testing and assessment of biomarkers of renal damage every 2 weeks, and must not receive Study Drug if there are no test results for parameters considered critical to patient safety available within the prior 2 weeks. In such a case, the Investigator must contact the patient to hold dosing until these or new tests are obtained and reviewed.

Adherence to the program will be closely monitored by the Sponsor, and patients and trial sites that are unable or unwilling to comply with this important risk mitigation program will be discontinued from the study.

Patients should be informed of the possibility and risks of a reduction in platelet count, and of potential hepatic and renal risks, and the importance of adherence to the monitoring program. Any case of a platelet count reduction to levels below 50,000/mm^3 (Grade 3 or Grade 4) is considered an adverse event of special interest and should be reported in an expedited fashion to the Sponsor.

## **9. SERIOUS AND NON-SERIOUS ADVERSE EVENT REPORTING**

### **9.1 Sponsor Review of Safety Information**

Safety information will be collected, reviewed, and evaluated by the Sponsor or designee in accordance with the Safety Management Plan throughout the conduct of the clinical trial.

### **9.2 Regulatory Requirements**

The Sponsor or designee is responsible for regulatory submissions and reporting to the Investigators of suspected unexpected serious adverse reactions (SUSARs) per the International Conference on Harmonization (ICH) guidelines E2A and ICH E6. Country-specific regulatory requirements will be followed in accordance with local country regulations and guidelines.

Institutional Review Boards (IRB)/Independent Ethics Committees (IEC) will be notified of any SAE according to applicable regulations.

In addition to the Investigator's assessment of relatedness, the Sponsor or designee will evaluate the available information and perform an independent assessment of relatedness. While the Sponsor may upgrade an Investigator's decision it is not permissible to downgrade the Investigator's opinion for the purposes of determining whether the SAE meets the definition of a SUSAR.

Appropriate personnel at the Sponsor or designee will unblind SUSARs for the purpose of regulatory reporting. The Sponsor or designee will submit SUSARs to Regulatory Agencies in blinded or unblinded fashion according to local law.

